### 2.2. Primary Objective(s)

1. To determine whether RV increases expression of IL-25 transcripts by nasal epithelial cells in the asthma and AR but not control cohorts at the peak of infection (days 3 and 4).
2. To determine whether RV increases lower respiratory symptoms in the asthma but not AR and control cohorts.
3. To determine whether asthmatics and allergic rhinitics will demonstrate an increased severity of infection in comparison to control subjects.

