### Primary Outcomes

1. RV-induced expression of IL-25 mRNA transcripts in the asthma and AR cohorts versus healthy controls as determined in nasal scraping samples obtained on days 3 and 4 (compared to day 0) as determined by qPCR.
2. RV-induced lower respiratory symptoms in the asthma cohort versus AR and healthy control as determined using modified Jackson scores (1) that will include cough, chest tightness, wheezing, and shortness of breath as well as via the asthma control test (ACT).
3. Severity of infection in the asthma and AR cohorts versus healthy controls as quantified by viral load present in nasal secretion samples as determined by qPCR performed on days 1, 2, 3, 4, 7

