**Units of analysis:** The day 0  $\log_e$ (IL-25 qPCR expression) measurements will be subtracted from the post-challenge day 1, 2, 3, 4, and 7  $\log_e$ (IL-25 qPCR expression) measurements and these *subject-specific* pre- versus post-challenge changes in  $\log_e$ (IL-25 qPCR expression) will be the units of analysis. **Analytical approach:** The changes in  $\log_e$ (IL-25 qPCR expression) on post-challenge days 1, 2, 3, 4, and 7 will be analyzed as repeated measures by way of a linear mixed model (LMM). **LMM fixed effects:** Two sources of variability in the pre- versus post-challenge changes in  $\log_e$ (IL-25 qPCR expression) will be of primary interest. One source of variability will be the study-group to study-group variability (i.e. asthmatics, allergic rhinitis controls, and healthy-controls) in the changes in  $\log_e$ (IL-25 qPCR expression), while the other source of variability will be the post-challenge day to day variability in the changes in  $\log_e$ (IL-25 qPCR expression). **Concomitant variable variability:** Variability in the  $\log_e$ (IL-25 qPCR expression) changes due to inherent differences in day 0  $\log_e$ (IL-25 qPCR expression) will be extracted from the residual error to increase statistical power. **Random effects:** *Subject-specific* and *time-specific* random effects will be incorporated into the LMM to allow *intra-subject* measurement correlation to be accounted for in variance estimation and hypothesis testing. **Hypothesis testing:** *Between-study-group comparisons:* With regard to hypothesis testing, the pivotal comparisons will be the *between* study-group comparisons of the mean changes in  $\log_e$ (IL-25 qPCR expression) on post-challenge study days 3 and 4 when cold symptoms are expected to peak. More specifically, we will compare if the study-day 3 and study-day 4 mean changes in  $\log_e$ (IL-25 qPCR expression) differ between the 3 different underlying study-populations after taking into account the inherent variability in challenge study-day 0  $\log_e$ (IL-25 qPCR expression). These comparisons will require conducting a total of 6 hypothesis tests (i.e. 3 per study day), and in order to maintain an *intraday* experimental-type I error rate of 0.05, the null hypothesis rejection rule for the “*intraday*” *between-group* comparisons will be based on a Bonferroni corrected two-sided  $p \leq 0.0167$  (i.e.  $0.05/3$ ) rejection rule. *Within-study-group comparisons:* On a per *study-group* basis, we will conduct statistical tests to determine if the means of the  $\log_e$ (IL-25 qPCR expression) distributions on post-challenge days 1, 2, 3, 4, and 7, differ from the mean of the  $\log_e$ (cytokine expression) distribution on challenge study day 0. The *within-study-group* comparisons will be considered *secondary* in nature, and this set of comparisons will be primarily focused on the challenge study-day 3 and challenge study-day 4 changes in mean  $\log_e$ (IL-25 qPCR expression) when symptoms are expected to peak. More specifically, we will test if the mean of the  $\log_e$ (IL-25 qPCR expression) distribution is the same on challenge study-day 0 and challenge study-day 3 and if the mean of the  $\log_e$ (IL-25 qPCR expression) distribution is the same on challenge study-day 0 and challenge study-day 4. A Bonferroni corrected two-sided  $p \leq 0.025$  (i.e.  $0.05/2$ ) decision rule will be utilized as the null hypothesis rejection criterion for this set of tests. **Confidence intervals:** To aid in data interpretation, a 95% confidence interval will be constructed for each *between-group* comparison and for each *within-group* comparison. **Scale of interpretation:** The point-estimate and the lower and the upper 95% confidence interval limits will be anti-log transformed so that point-estimate and the lower and the upper limits of the 95% confidence interval represent ratios of geometric mean cytokine expression. **Alternative analytical approach:** If the linear mixed model assumptions are deemed to be violated for this endpoint, we will use a linear mixed model based permutation test strategy to derive empirical based *distribution free* tests for testing the aforementioned *between-group* and *within-group* hypotheses.

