#### 13.6 Statistical Hypotheses

All of the hypotheses related to the primary and secondary outcomes will be two-sided. Three types of hypothesis tests will be conducted. The underlying motivation of one set of hypotheses (*between-group comparisons*) will be to examine if the distributions of the outcome random variable in the underlying study populations of the 3 study groups share the same location parameter value (e.g. mean, geometric mean). The underlying motivation of a second set of hypotheses (*within-group comparisons*) will be to examine if the underlying distributions of the outcome random variable pre- and post- RV challenge share the same location parameter value, and the underlying motivation of a third set of hypotheses (*bivariate-correlation*) will be to examine if the bivariate correlation between two random outcome variables is zero.

*Between-group comparisons*: With regard to the *between-group* comparisons, for each primary and secondary outcome variable the central *null hypothesis* is that the location parameter values (i.e. means or geometric means) of underlying distributions of the 3 study populations (i.e. asthmatics, allergic rhinitis controls, healthy-controls) are the same, whereas the *alternative hypothesis* is that at the underlying distributions of the 3 study populations have location parameter values that are not the same.

*Within-group comparisons*: With regard to the *within-group* comparisons, for each primary and secondary outcome variable the *null hypothesis* is that the underlying value of distribution location parameter (i.e. means or geometric means) is the same before and after RV-challenge, whereas the *alternative hypothesis* is that the underlying value of the distribution location parameter is not the same before and after RV-challenge.

*Bivariate-correlation*: With regard to bivariate correlation, the *null hypothesis* is that the underlying correlation between the two outcome random variables is zero, whereas the *alternative hypothesis* is that the underlying correlation between the two outcome random variables is non-zero.

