#### 13.7 Sample Size Considerations

**Overview (Aim 1):** The primary null hypotheses of Aim 1 will test if the pre- to post-challenge day-3 and day-4 changes in ex vivo IL-25 are the same for allergic asthmatics, allergic-rhinitis-controls, and health controls.

**Hypothesis testing:** To combine the post-challenge day-3 and day-4 comparisons we will first construct a 4 degree of freedom linear contrast of means to test the “global” null hypothesis that irrespective of the study group, the mean pre- to post-challenge day-3 change in  $\log_e(\text{IL-25})$  (i.e.  $\Delta \log_e(\text{IL-25})_{[\text{Day } 3]} = \log_e(\text{IL-25}_{\text{Post} [\text{Day } 3]}) - \log_e(\text{IL-25}_{\text{Pre} [\text{Day } 0]})$ ) is the same, and irrespective of the study group, the mean pre to post-challenge day-4 change in  $\log_e(\text{IL-25})$  (i.e.  $\Delta \log_e(\text{IL-25})_{[\text{Day } 4]} = \log_e(\text{IL-25}_{\text{Post} [\text{Day } 4]}) - \log_e(\text{IL-25}_{\text{Pre} [\text{Day } 0]})$ ) is the same. **Scenario #1:** If this “global” null hypothesis fails to be rejected at the  $p \leq 0.05$  significance level, then no post-challenge day-3 or post-challenge day-4 between-group comparisons will be conducted. **Scenario #2:** If this “global” null

hypothesis is rejected at the  $p \leq 0.05$  significance level, then 3 linear contrasts of the post-challenge day-3 mean  $\Delta \log_e(\text{IL-25})_{[\text{Day } 3]}$  will be constructed to compare the mean  $\Delta \log_e(\text{IL-25})_{[\text{Day } 3]}$  between the 3 study-populations, and 3 linear contrasts of the post-challenge day-4 mean  $\Delta \log_e(\text{IL-25})_{[\text{Day } 4]}$  will be constructed to compare the mean  $\Delta \log_e(\text{IL-25})_{[\text{Day } 4]}$  between the 3 study-populations. Since under scenario # 2, three post-challenge day-3 between-group comparisons of mean  $\Delta \log_e(\text{IL-25})_{[\text{Day } 3]}$  will be conducted, a two-sided Bonferroni  $p \leq 0.05/3$  decision rule will be utilized as the null hypothesis rejection criterion for this set of between-group comparisons. Similarly, since under scenario #2 three post-challenge day-4 between-group comparisons will be conducted, a two-sided Bonferroni  $p \leq 0.05/3$  decision rule will be utilized as the null hypothesis rejection criterion for this set of between-group comparisons.

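### Sections 13.4.2 and 13.7 give different testing procedures for the primary IL-25 endpoint, and neither says whether one positive day or both is needed

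*Combined protocol and SAP*

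**What the plan says.** Objective 1 in section 2.2 places the IL-25 response "at the peak of infection (days 3 and 4"). Item 1 of Primary Outcomes lists it as a single endpoint, "as determined in nasal scraping samples obtained on days 3 and 4 (compared to day 0) as determined by qPCR".

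Section 13.4.2, headed as the primary analysis, makes the between-cohort comparisons on day 3 and on day 4 pivotal. There are three cohort pairs on each of two days: "These comparisons will require conducting a total of 6 hypothesis tests (i.e. 3 per study day"). Each is two-sided at 0.0167, chosen "in order to maintain an *intraday* experimental-type I error rate of 0.05". No earlier test has to succeed, and there is no correction across the two days.

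Section 13.7, under sample size, sets out another sequence for the day-3 and day-4 changes: "we will first construct a 4 degree of freedom linear contrast of means". If that test does not reach 0.05, "then no post-challenge day-3 or post-challenge day-4 between-group comparisons will be conducted". If it does, the six comparisons follow at 0.05/3 within each day.

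Power in 13.7 is stated per day: 20 per cohort, SD of the log change 0.12, alpha 0.05/3, power 0.80, detectable factor 1.14 (Table II).

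**The concern.** Two analysts could each follow the document faithfully and reach different conclusions. One who works from 13.4.2 may report a significant day-3 or day-4 pair even though the global test in 13.7 failed. One who works from 13.7 may not.

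The rule for success is also open. An endpoint defined over two days and tested once per day needs a statement of whether one positive day is enough. If one is enough, 13.4.2 gives two chances of a false claim, each controlled at 0.05. If both are needed, error is no longer an issue, but the power quoted for one day does not apply to the pair. The study is open label (section 3.4), so a rule left unsettled could be chosen with the results in view.

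**Working it through.** **Inputs.** From 13.7: n = 20 per cohort, SD of the change 0.12, pre/post correlation 0.30, alpha 0.05/3, power 0.80, factor 1.14. From 13.6: two-sided tests.

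**Plan's own figure.** Two-sample t-test, 38 df, alpha 0.0167, power 0.80: standardised difference 1.064. Factor = exp(0.12 × 1.064) = 1.136, which rounds to 1.14. Table II is reproduced.

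**Correlation between the day-3 and day-4 changes.** The documents do not give it. Let r be the correlation between the day-3 and day-4 measurements. Both changes share day 0, so with pre/post correlation 0.30 and equal variances the change correlation is (r − 0.30 − 0.30 + 1)/(2 − 2 × 0.30) = (r + 0.40)/1.40.
- r = 0.30 (assumed) gives 0.70/1.40 = 0.50.
- Adjusting for day 0 at the same r gives (0.30 − 0.09)/(1 − 0.09) = 0.23.
- r = 0.60 gives 1.00/1.40 = 0.71, and r = 0.72 gives 0.80.

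The range 0.23 to 0.8 is used below.

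**Method.** 200,000 simulated trials per setting, three cohorts of 20, bivariate normal changes, per-day t-tests with pooled variance (57 df). The global test is the Wilks F test on both days. This simplifies the mixed model but keeps the structure of the tests.

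**Error when all cohorts are equal (any of the six tests rejects)**

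| Change correlation | 13.4.2 alone | 13.7, global test first | Six tests at 0.05/6 |
|---|---|---|---|
| 0.23 | 0.084 | 0.042 | 0.044 |
| 0.5 | 0.080 | 0.039 | 0.043 |
| 0.7 | 0.073 | 0.034 | 0.039 |
| 0.8 | 0.070 | 0.033 | 0.038 |

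**Error when asthma and AR both differ from controls by 1.14 on day 4 only.** A false claim is any day-3 pair, or asthma versus AR on day 4. With the global test first the rate is 0.058, 0.057, 0.055 and 0.053 at the four correlations. The global test nearly always passes here, so it no longer protects the other tests. At 0.05/6 the rate is 0.030 to 0.027.

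**Power for one pair, factor 1.14 on both days (log difference 0.131, or 1.092 SD)**

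| Change correlation | Both days | Either day, 13.4.2 | Either day, 13.7 | Either day, 0.05/6 | Day 3-4 mean at 0.05/3 |
|---|---|---|---|---|---|
| 0.23 | 0.71 | 0.96 | 0.95 | 0.92 | 0.97 |
| 0.5 | 0.73 | 0.93 | 0.92 | 0.89 | 0.93 |
| 0.7 | 0.76 | 0.91 | 0.89 | 0.86 | 0.90 |
| 0.8 | 0.77 | 0.90 | 0.87 | 0.84 | 0.88 |

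One named day has power of about 0.83 to 0.84 throughout.

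**Power if the 1.14 difference is on day 4 only, correlation 0.5.** Either day with the global test first 0.83, either day at 0.05/6 0.76, mean contrast 0.33.

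**Detectable factor at 0.05/6.** Per day, 38 df: standardised difference 1.154, factor exp(0.12 × 1.154) = 1.148, about 1.15.

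**The case against.** The strongest reply is that the plan already joins the two days. The global test in 13.7 covers both at 0.05, and no daily comparison is made if it fails. A reader of 13.4.2 might infer that the trial's IL-25 error rate is 8%. The documents do not support that for the plan as a whole, because under 13.7 the rate with equal cohorts is about 3 to 4%. This stands, and it limits the 8% to 13.4.2 followed alone. It does not close the matter: the global test is absent from the section that defines the primary analysis, and it does not settle one day versus both. It also holds error below 0.05 only when no cohort differs on either day, although the excess otherwise is small.

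A second tempting inference is that daily testing wastes power and should give way to the day 3-4 mean. The mean does beat a named day, a both-days rule and an either-day rule at 0.05/6 when the response is similar on both days. But at correlation 0.5 it only equals the either-day rule of 13.4.2 and exceeds the 13.7 sequence by about one point. If the response falls on one day it is far weaker. The documents state power per day and do not claim equal responses on both.

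Nor is it right that the two days are never brought together: 13.4.2 fits all post-challenge days in one mixed model, and 13.7 tests days 3 and 4 jointly.

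**Conclusion.** The inconsistency is real and concerns a primary endpoint. Section 13.4.2 alone gives about 8% endpoint error (0.084 to 0.070). Section 13.7 gives about 3 to 4% with equal cohorts and 5 to 6% false claims when the response is confined to one day. The missing success rule matters as much: a both-days requirement has power of 0.71 to 0.77 at the 1.14 factor, short of 0.80.

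These figures rest on the plan's SD of 0.12 and n of 20, on normal changes, and on an assumed range for the day-3/day-4 correlation. They also take the IL-25 variable in 13.7, described there as ex vivo, to be the nasal-scraping endpoint. Section 13.7 calls it the primary endpoint and uses the same challenge days, so this is the natural reading. Replacing the daily tests with a mean contrast is not a required correction.

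**What to change.** State one procedure in 13.4.2 and make 13.7 refer to it. Either of these will do:

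1. Carry the 13.7 global test into 13.4.2 as the required first step, keep 0.05/3 within each day, and state that a significant pair on either day suffices. Table II stays as it is. The cost is the residual 5 to 6% false-claim rate if the response occurs on one day only.
2. Test the six day-specific comparisons at 0.05/6 with no prior global test, state that either day suffices, and restate the Table II factor as about 1.15. Endpoint error is then about 4% with equal cohorts and stays below 0.05 in the one-day case. The cost is the slightly larger detectable factor.

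Optional: if the investigators expect similar responses on both days, they may instead pre-specify the mixed-model contrast of the day 3-4 mean, with three pairs at 0.05/3 and the daily estimates secondary. At correlation 0.5 its power is 0.93 against 0.89 for option 2, but 0.33 against 0.83 for option 1 if the response is on day 4 only.

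All of this is a change of wording. No visits, samples or participants are added.

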Primary Endpoint(s)	
 
1. RV-induced expression of IL-25 mRNA transcripts in the asthma and AR cohorts versus healthy controls as determined in nasal scraping samples obtained on days 3 and 4 (compared to day 0) as determined by qPCR.
 
2. RV-induced lower respiratory symptoms in the asthma cohort versus AR and healthy control as determined using modified Jackson scores (1) that will include cough, chest tightness, wheezing, and shortness of breath as well as via the asthma control test (ACT).
 
3. Severity of infection in the asthma and AR cohorts versus healthy controls as quantified by viral load present in nasal secretion samples as determined by qPCR performed on days 1, 2, 3, 4, 7.
 

Secondary Endpoint(s)	
 
1. IL-25 transcript expression in nasal scraping samples obtained on days 1, 2, and 7 (as compared to day 0).
 
2. Expression by nasal epithelial cells of a type 2 cytokine-inducing profile will be determined by also evaluating the time course of IL-33 and TSLP transcript expression by qPCR on nasal scraping samples obtained on days 0, 1, 2, 3, 4 and 7.
 
3. Expression of this type 2 cytokine-inducing profile will be corroborated by evaluating IL-25, IL-33, and TSLP protein expression by EIA on nasal secretion samples obtained via immunosorbent sponge.
 
4. Airway inflammation will be determined as increases in circulating absolute eosinophil counts, increased FeNO, and as changes in methacholine PD20.
 
5. Severity of RV infection will be corroborated as increases in upper respiratory symptoms using modified Jackson scores (1).
 

	
This scoring system includes sneezing, nasal discharge, nasal obstruction, sore throat, headache, malaise, and chills.
 
6. Severity of RV infection will be correlated with decreased innate immunity as assessed as reduced IFN-<math>\alpha</math>, -<math>\beta</math>, -<math>\lambda</math>, and IL-15 measured as qPCR of nasal scrapings and as enzyme immunoassays (EIAs) of nasal secretions (sponge-derived samples).

Accrual Objective	60 (20 each controls, AR, and asthma)
Study Duration	5 years to enroll, 8- 12 weeks for each participant to complete the study
Treatment Description	Rhinovirus (GMP RV16 HRV-16) inoculation

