The total dose of RV-16 used in this study is expected to result in development of lower airway symptoms but not in either of the control cohorts, but will be safe in the study population of mild asthmatics proposed in this study. This is based on our previous investigations of 16 mild asthmatics and 9 controls challenged with a total dose of approximately 300TCID50 of rhinovirus 16 where we used a modification of the Jackson criteria to score daily upper and lower respiratory tract symptoms (1). Upper and lower respiratory scores were summarized for each individual by computing cumulative scores (CURTS and CLTRS) over study days 0 to 4 and over study days 0 to 21. The study showed that in both asthmatic patient groups (i.e., those with high IgE and those with low IgE), the lower respiratory tract symptoms scores were significantly increased ( $P < .001$ ) compared with control patients by day 21 (high IgE = 13.5 [6.2 to 29.3]; low IgE = 8.5 [3.2 to 22.3]; control patients = 0.7 [0.3 to 1.5]). Additionally, by day 4, the CLRTS scores for the asthmatic patients with high IgE were greater (mean [CI]: 4.2 [1.4 to 12.5]) than for the asthmatic patients with low IgE (1.0 [0.4 to 2.5,  $P = .05$ ]) and control patients (0.4 [0.2 to 1.2]  $P = .0003$  (low IgE group versus control patients,  $P = 0.2$ )). During the infection, all but 3 of the asthmatic subjects reported mild lower respiratory tract symptoms of cough, wheeze, shortness of

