breath, or chest discomfort and none of the asthmatic patients had symptoms requiring intervention with anti-inflammatory medications (i.e., inhaled or oral steroids). Also, on the basis of the modified Jackson criteria, the development of peak upper respiratory symptoms in asthmatic patients was in many cases delayed: for example, 8 of 9 control patients (89%) had peak symptoms during the first 4 days compared with 8 of 16 asthmatic patients (50%,  $P = .05$ ). Also, the delayed development of peak symptoms observed for the asthmatic patients was more pronounced in the low IgE group: i.e., 4 of 6 (67%) with high IgE levels had peak symptoms during the first 4 days compared with 4 of 10 (40%) of those with low IgE levels. During the 21 days of monitoring, asthmatic patients had cumulative symptom scores that were increased and prolonged compared with scores in control patients. The difference between scores for the high IgE group and control patients was significant ( $P < .02$ ); the difference between scores for the low IgE group and control patients was not significant.

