### **Between Visits 6 and 7 (Days 5 and 6)**

Subjects will complete the diary card daily

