### **Study Visit 8 (Day 14) – to occur within a +5 day window (D14 to D19)**

Fourteen (14) days after RV inoculation, subjects will return to complete the ACT questionnaire and to report any adverse events. In addition, a limited physical examination will be performed including chest auscultation and a final assessment of FeNO (asthmatics only)/spirometry will be performed. A repeat CBC & differential (3ml purple top) will be drawn if ANC or ALC fell below 500/ $\mu$ L Day 4. If subject is still symptomatic they will be contacted at day 21 with the possibility of an unscheduled visit.

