
**Analysis of RV-induced lower-respiratory symptoms:** The lower respiratory symptom scores from challenge study-days 0, 1, 2, 3, 4, and 7, will be analyzed in two different ways. In the first approach; due to the expected infrequency of lower respiratory symptoms in the allergic rhinitis and healthy control cohorts, cumulative lower respiratory total symptom (CLRTS) will be computed for challenge period; day 0 to day 4, and for challenge period; day 0 to day 7. In the second approach the daily total lower respiratory symptom scores will be analyzed.

**Analytical approach #1:** We will use the total lower respiratory symptom scores of challenge days 0, 1, 2, 3, and 4 to compute to a cumulative lower respiratory symptom score (CLRTS) for challenge period day 0 to day 4, and we will use the total lower respiratory symptom scores of challenge days 0, 1, 2, 3, 4, and 7 to compute a CLRTS for challenge period day 0 to day 7. **Analytical approach:** The CLRTS will be analyzed as integer scaled random variables by way of a Negative Binomial (NB) generalized estimating equation (GEE) model. **GEE model specification:** The GEE model specification for the CLRTS analysis will include two predictor variables. One predictor variable will identify the study-group (i.e. asthmatics, allergic rhinitis controls, and healthy-controls) while the other predictor variable will identify the challenge period (i.e. day 0 to day 4, or day 0 to day 7). **Variance estimation:** An “unstructured” variance-covariance matrix form will be utilized to account for the inherent correlation between the first set of CLRTS scores (challenge day 0 to challenge day 4) and the second set of CLRTS scores (challenge day 0 to challenge day 7). **Hypothesis testing:** Wald tests will be conducted to determine if the means of CLRTS distributions for each challenge period differ from study-population to study populations. A Bonferroni two-sided  $p \leq 0.0167$  (0.05/3) criterion will be utilized as the null hypothesis rejection rule for the intra-challenge-period, between-group comparisons.

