**Analytical approach #2:** We will analyze the lower respiratory total symptom scores for challenge days 0, 1, 2, 3, 4, and 7 as repeated measures in this approach. **Analytical approach:** The lower respiratory total symptom score data will be analyzed by way of a negative-binomial generalized estimating equation (GEE) model. **Model specification:** The GEE model specification will include two predictor variables. One predictor variable will identify the study-group (i.e. asthmatics, allergic rhinitis controls, and healthy-controls), while the other predictor variable will identify the challenge study-day (i.e. day 0, 1, 2, 3, 4, or 7). **Variance estimation:** A “working independence” variance covariance matrix form will be utilized to account for the inherent *intra-subject* measurement correlation induced by the repeated measures aspect of the RV challenge study design. **Hypothesis testing:** Wald chi-square tests will be utilized to test if the means of total lower symptom score distributions on a particular challenge day differed between the 3 different study-groups. The primary focus will be to determine if the means of total lower symptom score distributions differed between the 3 different study-groups on study-days 3 and 4, when symptoms are expected to peak.

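### Primary endpoint 2 analyses lower respiratory symptoms only to day 7, and without days 5 and 6, so it can understate a late asthmatic response

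*Combined protocol and SAP*

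**What the plan says.** The Protocol Synopsis defines primary endpoint 2 as "RV-induced lower respiratory symptoms in the asthma cohort versus AR and healthy control as determined using modified Jackson scores", together with the Asthma Control Test (ACT).

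Section 13.4.2 analyses the scores in two ways.
- Approach #1 takes a cumulative lower respiratory score ("CLRTS) will be computed for challenge period; day 0 to day 4, and for challenge period; day 0 to day 7"). Each window is tested at two-sided 0.05/3, and neither is ranked first. For the longer window, "we will use the total lower respiratory symptom scores of challenge days 0, 1, 2, 3, 4, and 7 to compute a CLRTS", so days 5 and 6 do not enter.
- Approach #2 models the daily scores and asks mainly whether means "differed between the 3 different study-groups on study-days 3 and 4, when symptoms are expected to peak".

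Collection runs somewhat wider than the analysis.
- For days 5 and 6, section 8.2 says "Subjects will complete the diary card daily".
- At day 14, "subjects will return to complete the ACT questionnaire and to report any adverse events", with an examination, spirometry and, in asthmatics, FeNO. That text has no diary review or Jackson score, although Table I marks a symptom assessment at days 14 and 21.
- Day 21 contact is only for subjects still symptomatic at day 14, or whose blood counts have not recovered.

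Section 13.4.2 uses nothing collected after day 7 and contains no ACT analysis. Section 13.7 gives no power for this endpoint.

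The evidence offered for the endpoint is the earlier RV16 challenge in section 1.3, which summarised symptoms by "computing cumulative scores (CURTS and CLTRS) over study days 0 to 4 and over study days 0 to 21".

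**The concern.** The earlier study is the plan's own basis for expecting lower airway symptoms in asthmatics. It used about the same dose and a modified Jackson score. Its long window ran to day 21, and the present plan stops at day 7. In that study the asthmatics' scores grew much more after day 4 than the controls' did. A short window may then keep most of the control signal and a minority of the asthmatic signal, which shrinks the contrast that the endpoint tests.

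Enrolment bears on this. Section 1.3 links detectable lower-symptom differences to screening on total IgE of at least 125 IU/ml. Section 4.2 admits asthmatics on a positive skin test with no total IgE threshold, so the group that was slower to separate can be enrolled. Scores that are never collected cannot be recovered at analysis.

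**Working it through.** **Inputs** (section 1.3; mean cumulative lower score with interval; 6 high-IgE asthmatics, 10 low-IgE asthmatics, 9 controls):

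| Group | Days 0-4 | Days 0-21 | Share by day 4 |
|---|---|---|---|
| High IgE | 4.2 [1.4, 12.5] | 13.5 [6.2, 29.3] | 4.2/13.5 = 31% |
| Low IgE | 1.0 [0.4, 2.5] | 8.5 [3.2, 22.3] | 1.0/8.5 = 12% |
| Control | 0.4 [0.2, 1.2] | 0.7 [0.3, 1.5] | 0.4/0.7 = 57% |

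The shares are ratios of group means. The asthma/control ratio rises from 1.0/0.4 = 2.5 to 8.5/0.7 = 12.1 (low IgE) and from 4.2/0.4 = 10.5 to 13.5/0.7 = 19.3 (high IgE).

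**Reproducing the reported tests.** I treat the intervals as 95% and symmetric on the log scale, so the SE of a log mean is ln(upper/lower)/3.92. At day 4 this gives 0.558, 0.467 and 0.457 (high, low, control). At day 21 it gives 0.396, 0.495 and 0.411. Wald tests on the log ratios:
- Day 4, low IgE v control: 0.916/√(0.467² + 0.457²) = 1.40, P = 0.16 (reported 0.2).
- Day 4, high v low IgE: P = 0.049 (reported .05).
- Day 4, high IgE v control: P = 0.001 (reported .0003; same conclusion from rounded inputs).
- Day 21, low and high IgE v control: P = 0.0001 and 2×10⁻⁷ (both reported <.001).

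The method recovers the published conclusions.

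**Illustrative power at 20 per group, two-sided 0.05/3 (critical z = 2.394).** Per-subject SD = SE × √n. At day 4 the SDs are 1.37 (high), 1.48 (low) and 1.37 (control). Power = Φ(ln ratio/√((s₁² + s₂²)/20) − 2.394).
- All low IgE: z = 0.916/0.451 = 2.03, power 36%.
- All high IgE: z = 5.43, power above 99%.
- 6:10 high:low mix: the variance is the weighted within-group variance plus (6/16)(10/16)(ln 4.2)² for the difference between subgroups. With a geometric mixed mean (ratio 4.28), power is 76%. With an arithmetic one (ratio 5.5), it is 89%.
- Day 0-21 window: above 99% in every case.

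**The day 0-7 window.** The documents give no day-7 value, so an accrual pattern must be assumed.
- *Late symptoms even over days 5-21.* With only day 7 added, the low-IgE score is 1.0 + 7.5/17 = 1.44 (17% of the 21-day total) and the high-IgE score is 4.2 + 9.3/17 = 4.75 (35%). Adding days 5 and 6 gives 1.0 + 3 × 7.5/17 = 2.32 (27%) and 5.84 (43%).
- *Late symptoms decaying from day 5 with a half-life of 2 to 5 days.* The score as defined holds 21-25% (low) and 39-41% (high). With days 5 and 6 it holds 45-69% and 57-76%.
- *Power, all low IgE.* Controls go to 0.4 + 0.3/17 = 0.418 under even accrual. The ratio is 3.45 and, with the day-4 SDs, z = 1.239/0.451 = 2.75, power 64%. Across the assumptions above the score as defined gives about 64-86%, and about 89-99% for the 6:10 mix. With days 5 and 6 included, even accrual gives 89% for all low IgE.

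**The case against.** The strongest reply has five parts.

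1. *The 36% figure belongs to one window and an extreme cohort.* It needs every asthmatic to be low IgE and ignores the 0-7 window, which is also tested. A low captured share is not the same as low power. This stands. A reader might infer that the endpoint is likely to fail, or that a negative result would be an artefact of the schedule. The documents do not support that: the only mix they report keeps 76-89% power even in the shorter window.

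2. *Much of the late accrual is window length.* Days 5-21 are 17 of 22 days (77%), and the 6:10 pooled mean accrues (10.375 − 2.2)/10.375 = 79% of its total then. Per day, high-IgE asthmatics scored more early (4.2/5 = 0.84) than late (9.3/17 = 0.55). Only the low-IgE group scored more late (0.20 v 0.44). This stands, and it blocks a second tempting inference, that the statement placing the symptom peak at days 3-4 is wrong. Cumulative totals cannot locate a daily peak. The delayed peaks in section 1.3 ("8 of 9 control patients (89%) had peak symptoms during the first 4 days compared with 8 of 16 asthmatic patients") concern upper respiratory symptoms and are only supporting evidence. Window length does not explain why controls had 57% of their total by day 4 and low-IgE asthmatics 12%.

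3. *Collection does not simply stop at day 7.* ACT is taken at day 14, Table I marks symptom assessments at days 14 and 21, and the diary has no stated end date. So it would be wrong to infer that no symptom data exist after day 7. What remains is that the visit text schedules no diary or Jackson score for all subjects after day 7, and none is analysed.

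4. *The evidence is thin.* The groups are 6, 10 and 9 with wide intervals, the earlier virus predates the GMP pool, and the day-4 P of 0.2 for low IgE is a non-significant 2.5-fold ratio, not proof of no difference. This stands and limits confidence.

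5. *An acute-phase focus matches the day 3-4 IL-25 hypothesis.* That is a defensible reason to keep the short windows, but not a reason to omit a longer one.

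**Conclusion.** The concern holds as a limited point. The planned windows can understate the asthma-control contrast on primary endpoint 2, chiefly if many low-IgE asthmatics enrol. For the day 0-4 window, illustrative power ranges from about 36% to above 99% with the IgE mix. For the day 0-7 window the loss cannot be determined from the documents, and leaving out days 5 and 6 adds to it. These figures assume log-symmetric 95% intervals, a normal approximation in place of the planned negative binomial model, and that the earlier small groups carry over to this cohort.

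The figure above 99% belongs to day 21. No day-14 value is given, so a reader should not infer that day 14 has been shown to be adequate, or that it must be the deciding window. This is a should-fix, not a must-fix: the existing windows are not invalid, but a primary endpoint can be made safer cheaply, and only prospectively.

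**What to change.** **Section 8.2.** Continue the existing diary through day 14 for all subjects and review it at Visit 8. Continue it to day 21 for those still symptomatic, who are to be contacted then anyway. This would also bring the visit text into line with the Table I symptom mark at day 14.

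**Section 13.4.2.**
- Include the day 5 and 6 scores, already recorded, in the day 0-7 cumulative score.
- Add a prespecified day 0-14 cumulative score, analysed in the same negative binomial GEE model alongside the 0-4 and 0-7 windows.
- State in advance which window decides. Otherwise three windows, each controlled at 0.05, allow up to 3 × 0.05 = 0.15 across windows.
- Say how missing second-week diary days are handled in the sum.

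The statement about a day 3-4 peak can stay.

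**Cost.** One more week of diary cards that participants already hold, some missing entries in that week, and a few lines of text. No new visit or procedure is needed. Including days 5 and 6 needs no further collection.
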